This is a quasi-experimental open trial enrolling parents and caregivers of individuals with first episode psychosis (FEP) receiving care from CSC clinics across North Carolina. Parents and caregivers in the Altitudes condition, which will be drawn from 2 CSC clinics (OASIS, SHORE), will participate in the use of Altitudes, a novel digital intervention, which has previously demonstrated benefits to this population in an Australian pilot trial. They will also complete psychological measures as part of the study. Participants in the control condition from 3 other CSC clinics in North Carolina (Eagle, Encompass, AEGIS) will not have access to the digital intervention but may engage with standard clinical services at the CSC clinics. The control participants will complete measures at the same time points as the open trial participants at OASIS and SHORE clinics.

Subject Population Key Criteria for Inclusion and Exclusion:

Inclusion criteria:

- 1) Parent or caregiver of a young person who is currently receiving treatment from a CSC program for FEP, or who have recently graduated from a CSC program
- 2) Parent or caregiver must be at least 18 years of age

- 3) Participants recruited from Outreach and Support Intervention Services (OASIS) & SHORE (Supporting Hope, Opportunities, Recovery and Empowerment; i.e., two CSC programs in NC), as this is a pilot study, or Eagle, Encompass, and AEGIS clinics for participants part of the control group
- 4) Parent or caregiver must have access to internet through a mobile phone, tablet, or computer

Exclusion criteria:

- 1) Parent or caregiver is currently engaged in legal action against the loved one receiving services from the CSC program
- 2) Parent or caregiver does not speak English
- 3) Parent or caregiver is under 18 years of age

Number of Subjects

Thirty parent or caregiver participants from OASIS and SHORE CSC clinics and 30 parent or caregiver participants from Eagle, Encompass, and AEGIS.

Study Duration

Each subject's participation will last approximately 6 months from baseline to post-treatment. The entire study is expected to last approximately 12 months (including a 6-month recruitment period).

Study Phases

Screening: Completed prior to the first virtual appointment via a telephone screen to confirm study eligibility.

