Information gathered in the post-treatment qualitative interview will be analyzed to identify participants' thoughts about the usefulness of Altitudes as well as feedback to improve the intervention for others. Qualitative analysis will be conducted on the feedback interviews using grounded theory. As with qualitative analysis, a codebook will be developed by the research team in which thematic analysis of all interviews will conducted. The codebook will include themes and subthemes with a focus on the different perceived strengths of the intervention as well as areas that need improvement.

Secondary Outcomes: The platform will collect information about frequency of engagement with Altitudes (i.e., site usage). Psychosocial outcomes will be summarized within and between conditions using univariate statistics (e.g., means, standard deviations). To evaluate change over time on psychosocial outcomes, we will utilize linear mixed models (LMM) including fixed effects of time, group, and group x time interactions and random effects at the participant level. We will calculate changes from baseline at each time point using least-squares means and standardized least-squares mean differences to estimate within- and between-group changes, respectively. To estimate magnitude of change from baseline, we will calculate effect sizes. We will explore the relationship between baseline characteristics (e.g., age, gender) and engagement data (i.e., site usage information) on any changes in psychosocial outcome measures from baseline to midpoint and posttreatment using multiple linear regression. We will use Pearsons correlation coefficients to examine associations between carers' involvement in Altitudes and their loved one with FEP's use of emergency services (e.g., ED visits). If possible based on sample size, we will dichotomize engagement data (site usage) between low engagement and high engagement before comparing site usage with emergency service utilization.

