The research study coordinator will communicate with clinicians and other members of the treatment team to explain the project and discuss eligibility criteria for the study. If agreed to by the clinical team at each site, the research team will attend the beginning or end of multifamily group (MFG) sessions at OASIS & SHORE to provide an overview of Altitudes and answer any questions that potential participants might have about the study. Research staff will additionally contact the other three clinics (Eagle, Encompass, AEGIS, and We2Care) about control participants and attend their MFG to provide information to prospective participants. Clinical team members will be asked to review their current caseloads to identify potentially eligible participants (i.e., parents and caregivers of patients who are currently receiving services or recently graduated from one of the programs). The study coordinator and/or research assistant (RA) will engage in discussion with the treatment team to help identify appropriate individuals for inclusion in the project. When participants have been identified and expressed interest in participation to their clinician or other treatment provider, the research study coordinator or RA will reach out to the individual in their preferred method of contact (i.e., in person at the clinic or via phone/email) to discuss the project and complete an initial screen to confirm the inclusion and exclusion criteria. Participants will then be

given the highlights of the study and their participation via phone after their screening. Highlights will include the study, its aims, what they will be asked to do, the timeframe of their participation, and that it is completely voluntary and they can withdraw consent at any time, for any reason, without penalty. Additionally, in the email to review the document and at the top of the consent forms in DocuSign there will be a phone number for them to contact and explicitly state to call the number if they have any questions prior to signing the documents.

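### Condition is set by whole clinic, but the mixed model carries random effects only for participants, so group-by-time contrasts are overprecise if carers' change differs between clinics

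*Combined protocol and SAP*

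**What the plan says.** The Study Design section of the synopsis describes the trial as follows: "This is a quasi-experimental open trial enrolling parents and caregivers". Clinic decides condition. Number of Subjects gives "Thirty parent or caregiver participants from OASIS and SHORE CSC clinics and 30 parent or caregiver participants from Eagle, Encompass, and AEGIS", and Study Design adds: "Participants in the control condition from 3 other CSC clinics in North Carolina (Eagle, Encompass, AEGIS) will not have access". The Subjects and Eligibility Criteria sections repeat this arrangement. Screening Procedures differs: it refers to "the other three clinics (Eagle, Encompass, AEGIS, and We2Care", which counts three clinics but lists four.

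The between-group model appears once, under Secondary Outcomes in the synopsis Statistical and Analytic Plan: "To evaluate change over time on psychosocial outcomes, we will utilize linear mixed models (LMM) including fixed effects of time, group", continuing with "group x time interactions and random effects at the participant level". Its outputs are least-squares mean changes from baseline, standardised between-group differences and effect sizes. The Exploratory Outcomes paragraph applies the same model to trauma symptoms and post-traumatic growth.

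There is no clinic effect, clinic-by-time effect, cluster-robust standard error, degrees-of-freedom method or intraclass correlation anywhere. Clinic is also absent from the possible covariates listed under Subjects.

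**The concern.** Every carer at a given clinic is in the same condition, so the unit that carries the condition is the clinic, and there are five or six of them. Carers at one clinic share staff, multifamily groups and local services during the six months over which change is measured, so their changes may move together. The model counts carers as independent once each has a participant effect. Clinic-to-clinic variation in change would then enter the group-by-time estimate without entering its standard error.

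This matters because the control comparison has a stated purpose. The Objectives section says it will make the efficacy evaluation more rigorous, the Outcomes section hypothesises improvement relative to controls, and Power Analysis says the study will inform later, adequately powered trials. Overprecise effect sizes would carry into that planning.

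**Working it through.** The plan states no standard error, alpha, ICC or degrees of freedom, so there is no figure of its own to reproduce.

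**Inputs from the documents:** 30 + 30 carers; 2 Altitudes clinics; 3 control clinics (4 if We2Care recruits); three visits; random effects for participants only.

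**Assumptions:** two-sided 5% tests, no dropout, change-score SD of 1, carers spread evenly over clinics unless stated, and a clinic ICC of change between 0 and 0.10.

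**Degrees of freedom.** Participant level, one change score each: 60 − 2 = 58, critical t 2.00. A three-visit random-intercept model could use 2 × 58 = 116 for group-by-time. Clinic level: 5 − 2 = 3, critical t 3.18; with a fourth control clinic, 6 − 2 = 4, critical t 2.78.

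**Variance of the group difference in mean change, 15/15 versus 10/10/10.**
- Participant-level model: 1/30 + 1/30 = 1/15, so SE = 0.258 SD.
- With clinic variation: ICC × (1/2 + 1/3) + (1 − ICC)/15.
- Ratio: 15 × ICC × 5/6 + 1 − ICC = 1 + 11.5 × ICC.

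| Assumed ICC of change | SE factor | True SE (SD) | Type I error at nominal 5% | 95% half-width on 3 df (SD) |
|---|---|---|---|---|
| 0 | 1.00 | 0.258 | 5.0% | 0.82 |
| 0.01 | 1.06 | 0.273 | 6.4% | 0.87 |
| 0.02 | 1.11 | 0.286 | 7.8% | 0.91 |
| 0.05 | 1.25 | 0.324 | 11.9% | 1.03 |
| 0.10 | 1.47 | 0.379 | 18.8% | 1.20 |

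Type I error was simulated using t on 58 df; repeated runs agree to about 0.3 percentage points. The half-width is 3.18 × true SE. The participant-level half-width is 2.00 × 0.258 = 0.52 SD in every row.

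**Uneven enrolment (illustrative), 25/5 versus 20/5/5.** The sum of squared clinic shares is 650/900 + 450/900 = 1.222, so the ratio is 15 × 1.222 × ICC + 1 − ICC = 1 + 17.3 × ICC. Type I error is about 9.2% at ICC 0.02 and 15.3% at 0.05.

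**Four control clinics, 15/15 versus 8/8/7/7.** The sum is 1/2 + 226/900 = 0.751, so the ratio is 1 + 10.3 × ICC. At ICC 0.05 the SE factor is 1.23, against 1.25 with three.

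**Which clinic term matters.** Data were simulated for three visits and analysed with a participant random intercept.
- A clinic effect that is constant over time (5% of variance) cancels from change from baseline. The change contrast rejects in 5.2% of runs, although the overall group effect rejects in 15.0%.
- Clinic-by-time variance of 2.5% with residual 47.5% gives an ICC of change of 0.025/(0.025 + 0.475) = 0.05. The change contrast rejects in 12.2%.
- Clinic-by-time variance of 5% with residual 45% gives 0.05/0.50 = 0.10, and 18.9%.

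The last two agree with the table. The relevant term is clinic-by-time.

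**The case against.** The best defence is that the plan promises estimates and not tests. The analysis text names no p-value, confidence interval, alpha or degrees-of-freedom method; the between-group comparison is secondary or exploratory; the study is a pilot with no power calculation; and the design is openly called quasi-experimental. This limits the stakes. It also means that the type I error figures describe what would follow if the model's standard errors were used for testing, and that 58 df is illustrative. It does not remove the point: a mixed model yields standard errors, any statement of precision will draw on them, and the Objectives section ties this comparison to efficacy.

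A second objection is that no clinic ICC is known. That stands. A reader might infer that the standard errors are certainly too small and that every between-group interval will be too narrow. The documents do not support this: at an ICC of change of 0 the participant-level standard error is correct. Only the degrees-of-freedom mismatch is independent of the ICC.

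Third, the more serious weakness of two sets of non-randomised clinics may be confounding of clinic with condition. That is also true, and a wider interval does not cure it. It is a separate problem from the missing error term, as is the possible co-enrolment of relatives.

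**Conclusion.** The concern holds conditionally. The model omits the level at which condition is set, and following it exactly gives overprecise group-by-time contrasts whenever clinics differ in change. For evenly spread carers and ICCs of 0.01 to 0.10, the standard error is understated by a factor of 1.06 to 1.47 and a nominal 5% test runs at about 6.4% to 18.8%. Uneven clinic sizes make this worse; a fourth control clinic eases it slightly. These sizes rest on assumed ICCs, assumed clinic sizes and no dropout. What does not rest on them is that the contrast has 3 clinic-level degrees of freedom (4 with We2Care), against roughly 58 or more for participants.

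It would go too far to conclude that the platform comparison is shown to be inflated, or that the pilot's main results are compromised. The primary outcomes are descriptive and confined to the Altitudes group. The point is worth correcting before analysis; it does not threaten the pilot's main purpose.

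**What to change.** 1. Reconcile the clinic list in Screening Procedures with Study Design, Subjects and Eligibility Criteria, so that the number of control clinics is settled.
2. Add to the Secondary Outcomes analysis paragraph, and by reference to Exploratory Outcomes, a table of mean change and number of carers for each clinic at each follow-up visit.
3. Beside each between-group contrast, report (a) a comparison of clinic means on (number of clinics − 2) degrees of freedom and (b) the model's standard error recomputed, with the actual clinic sizes, over a stated and openly assumed ICC range such as 0 to 0.10.
4. Describe the contrast as a difference between clinics that did and did not offer Altitudes. Label any p-value or interval from the participant-level model as ignoring clinic.

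Adding only a random clinic intercept is not a repair: it cancels from change from baseline, and five or six clinics estimate a clinic variance poorly in any case.

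The cost is some plan wording, one extra table and wider intervals. No further data, clinics or participants are needed. Confounding of clinic with condition remains and should be stated as a limitation.

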Exploratory Outcomes: We will use descriptive statistics (M, SD) to examine self-reported trauma symptoms among carers of individuals with FEP. Descriptive statistics (M, SD, & effect sizes) will also be used to examine any changes in posttraumatic growth from baseline to midpoint and baseline to post-treatment. We will evaluate change over time in trauma-related symptoms and post-traumatic growth both within- and betweengroups using LMMs in the same manner as specified in our analysis of secondary outcomes. We will explore the relationship between baseline characteristics (e.g., age, gender) and engagement data (i.e., site usage information) on any changes in trauma-related symptoms and posttraumatic growth orientation over time.

Data and Safety Monitoring Plan

Privacy and online safety will be managed in accordance with the 'Online social networking' guidelines published by 'Cybersmart', a national cybersafety and cybersecurity education program managed by the Australian Communications and Media Authority (ACMA). Online safety will be monitored by Altitudes moderators (clinicians involved in the project, family peer support workers, graduate students in the Department of Psychology and Neuroscience) with supervision from licensed clinical psychologists Drs. [name] and [name]. [name] will function as the Project Medical Officer.

INTRODUCTION

Background and Rationale

Psychosis is one of the most debilitating health conditions, both mental or physical disorders, with significant impact on the individual as well as their family and supports. In response to these psychiatric disorders, known as schizophrenia-spectrum disorders, and to circumvent poor outcomes, early intervention services for first episode psychosis

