As this platform will be provided as an adjunct to CSC clinical care, pertinent clinical impressions and other relevant clinical information will be shared with the individual's clinical team at their respective FEP clinic.

All individual interviews will be conducted virtually via secure Zoom and will be led by the Altitudes study coordinator and/or a graduate student in clinical psychology at UNC-Chapel Hill. All feedback sessions will be digitally recorded, and will be de-identified and transcribed by a member of the research team or a transcription service. The purpose of these recordings and transcriptions is to allow the research team to examine the feedback provided in the interviews for the purposes of improving the platform to better support families and caregivers in supporting their loved ones experiencing psychosis via psychoeducation and skills such as healthy coping mechanisms.

Subjects

Up to 30 total Altitudes participants will be recruited from two of the FEP clinics in North Carolina (OASIS & SHORE) as it is a pilot study, specifically family members of individuals experiencing FEP. An additional 30 control participants will be recruited from three other FEP clinics in North Carolina (Eagle, Encompass, and AEGIS). All participants will have a loved one currently enrolled in or recently graduated from a CSC program. Demographic and clinical information that will be collected as self-report for possible use as covariates includes: 1) participant demographics: age, sex/gender identity, race/ethnicity, level of education, current zip code, relationship to loved one, employment status, proximity to the loved one with psychosis (e.g., cohabitating, living in different states), hours of contact with loved one per week on average, number and ages of any other children; and 2) young person with psychosis' demographics and relevant clinical information: age, sex/gender identity, level of education, stage of recovery, and level of education.

Eligibility Criteria

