Inclusion criteria for the study will be family (i.e., parent or other loved one in a caregiving role such as a grandparent, godparent, etc.) of a young person who is currently receiving treatment from a CSC program for first episode psychosis, or who have recently graduated from a CSC program. For the parent or caregiver to be eligible, the parent or caregiver must be at least 18 years of age. More than one family member will be eligible to participate from each family. Altitudes participants will be recruited from only two North Carolina CSC programs (OASIS & SHORE), as this is a pilot study, while the control participants will be recruited from three other CSC programs (Eagle, Encompass, and

AEGIS). Additionally, the parent/caregiver must have access to the internet through a mobile phone, tablet, or computer.

Exclusion criteria: Family who are currently engaged in legal action against the identified individual, do not speak English, or under 18 years of age.

ASSESSMENT OF DATA

At this stage of treatment development, specific outcomes include examining the feasibility and acceptability of implementing Altitudes at NC FEP clinics for parents and caregivers through the following objectives:

- 1) Ability to meet our recruitment targets
- 2) Evaluation of the safety and privacy protocol
- 3) Evaluation of the frequency and types of engagement on Altitudes
- 4) Examination of carers' perceptions of the platform (e.g., its utility, approachability, and helpfulness)
- 5) Assessment of any changes in psychological measures across the six-month intervention

Outcomes

We hypothesize that caregivers of individuals with psychosis will utilize the Altitudes platform and perceive it to be useful and beneficial for their understanding of their loved one's mental health issues. We also hypothesize that engagement in Altitudes will contribute to increased utilization of adaptive coping strategies, reduced expressed emotion in the familial milieu, and improved understanding of psychosis in comparison to the control participants.

STUDY PROCEDURES

Screening Procedures

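### Several carers per family may enrol, but the mixed model has no family term, so standard errors for the secondary and exploratory group comparisons may be too small

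*Combined protocol and SAP*

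**What the plan says.** Under Eligibility Criteria the combined protocol and SAP states: "More than one family member will be eligible to participate from each family". It sets no cap and gives no expected number.

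The Synopsis (Statistical and Analytic Plan, Secondary Outcomes) specifies a linear mixed model with "fixed effects of time, group, and group x time interactions and random effects at the participant level". The quantities to be reported are changes: "We will calculate changes from baseline at each time point using least-squares means", together with "standardized least-squares mean differences to estimate within- and between-group changes, respectively". The Exploratory Outcomes paragraph handles trauma symptoms and post-traumatic growth "using LMMs in the same manner as specified in our analysis of secondary outcomes".

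The Secondary Outcomes paragraph also plans a multiple linear regression of change on baseline characteristics and site usage. For the loved one's emergency-service use it says: "We will use Pearsons correlation coefficients to examine associations between" carers' involvement in the platform and that use.

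No section mentions a family random effect, clustered standard errors, an analysis set with one carer per family, or a sensitivity analysis for families. The Data Analytic Plan lists outcome measures and does not return to the model. The variables listed under Subjects and Baseline Procedures include no family identifier.

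**The concern.** Two carers of the same young person respond to the same illness course and, on several scales, rate the same person. Group is set by clinic, so relatives recruited through one clinic fall in the same group. Positive correlation between them then inflates the variance of a group mean, and a model with participant effects only does not see it.

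Co-enrolment is realistic, because recruitment runs through multifamily group sessions and clinic caseloads (Screening Procedures). Correlated change fits the protocol's own hypothesis, which expects expressed emotion to fall in the family setting as a whole.

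At stake is the stated precision of the secondary and exploratory changes and effect sizes. The Power Analysis section says the study is meant to feed the planning of later, powered trials, so those who plan them would work from these figures. Without a family identifier they also could not tell how many families the 60 carers represent, or estimate a family ICC.

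**Working it through.** **Inputs from the documents.** 30 carers per group (Synopsis, Number of Subjects), three visits, group determined by clinic, no limit on carers per family. The plan states no power, SD, ICC or precision, so it has no figure of its own to reproduce.

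**Assumed inputs.** At most two carers per family; 3, 6, 10 or 15 pairs per group (20%, 40%, 67%, 100% of carers); within-family ICC of the *change* of 0.1, 0.3 or 0.5. The plan gives no significance level. A nominal two-sided 5% test is used only to translate the understated standard error.

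**Step 1: design effect.** DE = 1 + (Σm²/N − 1) × ICC, where m is the number of carers in a family and N = 30. With 6 pairs and 18 single carers, Σm² = 6×4 + 18×1 = 42, and the bracket is 42/30 − 1 = 0.40. For 3, 10 and 15 pairs it is 36/30 − 1 = 0.20, 50/30 − 1 = 0.667 and 60/30 − 1 = 1.00. The SE ratio (true to model) is √DE, and type I error is 2 × P(Z > 1.96/√DE).

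| Pairs per group | ICC 0.1 | ICC 0.3 | ICC 0.5 |
|---|---|---|---|
| 3 | 1.01; 5.2% | 1.03; 5.7% | 1.05; 6.2% |
| 6 | 1.02; 5.5% | 1.06; 6.4% | 1.10; 7.4% |
| 10 | 1.03; 5.8% | 1.10; 7.4% | 1.15; 9.0% |
| 15 | 1.05; 6.2% | 1.14; 8.6% | 1.22; 11.0% |

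Each cell gives the SE ratio, then the type I error. Effective sample size per group is 30/DE: 29.4 in the mildest cell, 30/1.12 = 26.8 for 6 pairs at ICC 0.3, and 30/1.50 = 20.0 in the worst.

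**Step 2: check by simulation.** A two-sample t test on change (60,000 runs, complete data) gave 5.3% for 3 pairs at ICC 0.1, 6.5% for 6 pairs at 0.3, and 11.3% for 15 pairs at 0.5. A separate simulation of the planned participant-random-intercept contrast from baseline to month 6 (8,000 runs per scenario) covered 40% to 100% of carers in pairs and ICC 0.1 to 0.5. It gave SE ratios of 1.03 to 1.23 and type I error of 5.7% to 11.2%. Both agree with the table.

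**Step 3: family differences that do not change over time.** With variance 0.3 family, 0.3 participant and 0.4 residual (assumed), the family part cancels from the change contrast: SE ratio 1.00, type I error 4.8% to 5.1%. A group comparison at a single visit is still affected: SE ratio 1.03 to 1.15 and type I error 5.7%, 6.4%, 7.2% and 8.6% for 3, 6, 10 and 15 pairs.

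**Step 4: emergency-service correlation.** The outcome belongs to the young person. With 10 pairs among 30 Altitudes carers, 30 rows describe 30 − 10 = 20 young people. With the outcome identical within a family, simulated type I error is 5.0% to 5.2% (3 pairs, usage ICC 0.1), 7.2% to 7.6% (10 pairs, 0.3) and 11.4% to 11.6% (15 pairs, 0.5). It stays at 5% if usage is uncorrelated within families.

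**The case against.** The main planned contrast is change from baseline, which stable family differences leave untouched. Harm therefore needs both a fair number of co-enrolled relatives and positively correlated changes, and the documents establish neither. Carers need not live together: the covariate list under Subjects allows for relatives in different states. With 3 to 6 pairs and ICC 0.1 to 0.3 the standard error is only 1% to 6% too small; the worst figures need every carer to be paired. Negative correlation would make the standard error too large. This is also an exploratory pilot with no stated significance level or interval, and point estimates barely move. All of that stands. It limits the size of the problem, but the stated model still assumes independence that the eligibility rule does not support.

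Four narrower points also have force:

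- The single-visit figures concern a comparison that the plan does not clearly specify.
- The variable lists are not a data dictionary, so the safe statement is that no family identifier is mentioned.
- The source of emergency-service data is not given. Two carers' own reports could differ, although they would still describe one person's use.
- The planned regression of change scores is exposed in the same way as the mixed model and belongs in the remedy.

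**Conclusion.** The concern holds and should be fixed before analysis. As written, the model treats relatives in the same group as independent, and nothing elsewhere in the document repairs this. The consequence is conditional: standard errors for change are understated by 1% to 22% (type I error 5.2% to 11.0%) over 3 to 15 pairs per group and a change ICC of 0.1 to 0.5. They are not understated if relatives' changes are uncorrelated. Confidence is high about the gap in the text; the size cannot be fixed from the documents. The primary outcomes describe the Altitudes group only and are unaffected.

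A separate limitation is that group is fully determined by clinic, two against three. No model term, at family level or otherwise, can separate clinic from intervention.

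**What to change.** - Record a family identifier at enrolment. Report families and carers per family by group.
- Use family-clustered standard errors with a small-sample correction for all mixed-model contrasts and for the change-score regression. The alternative is a family random intercept plus a family-by-visit term, if estimable. A family intercept alone would not correct the change contrast.
- Add a sensitivity analysis with one carer per family, chosen by a rule fixed in advance, such as first enrolled.
- Analyse emergency-service use with one row per young person, combining the carers' usage. State where the emergency-service data come from.
- Report changes by clinic descriptively, and state that clinic and intervention effects cannot be separated.

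**Cost.** One variable and a few sentences. Intervals widen by about 1% to 22% over the assumed range, slightly more with the small-sample correction. In the worst case there are 30 families; taking families minus 2 as degrees of freedom (illustrative), the ratio is 1.225 × 2.048/2.002 = 1.25. With 3 to 15 pairs per group there are 2 × 27 = 54 down to 2 × 15 = 30 families, so clustered errors are workable. A family variance component may be poorly estimated if pairs are few.

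A formal clinic-level comparison is not advised. It would have 5 − 2 = 3 degrees of freedom and intervals about 1.63 to 2.25 times as wide (assuming 15/15 against 10/10/10 carers and a clinic ICC of 0.01 to 0.10).
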